PROJECT DESCRIPTION

Title: Attenuation of Stress Response Using Progesterone in Individuals with Alcohol Dependence and Post-Traumatic Stress Disorder NCT02187224

1. Principal Investigator:

[name]

Authorized Prescribers: [name] MD, [name] MD, [name] MD, [name] MD

2. Purpose:

Primary Aims:

1. To test if progesterone (PROG) is more effective than placebo in reducing craving after exposure to trauma or stress cues in a laboratory paradigm among men and women with a) comorbid AUD and PTSD and b) AUD only.

We hypothesize that progesterone in comparison to placebo will significantly reduce craving for alcohol in response to trauma cues in individuals with a) comorbid AUD and PTSD and b) AUD only. Craving for alcohol will be measured using a self-report Visual Analog Scale - Craving (VASC) and the Alcohol Urge Questionnaire (AUQ).

Secondary Aims:

1. To test if progesterone attenuates stress-induced anxiety, measured by the State Trait Anxiety Inventory (STAI-6).

2: To describe PROG's subjective mood effects, we will use the Differential Emotion Scale (DES-R)

3: To describe PROG's effects on cognitive performance, we will assess the ability to inhibit incongruent competing conflicts using the Stroop Color/Word test (Stroop).

Exploratory Aims:

1. To test if progesterone is more effective than placebo in reducing drinking and relapse during one month following exposure to trauma cues *using the Timeline Follow Back Method (TLFB)*.

2. To examine if there are gender differences in progesterone effects on stress and alcohol cue-induced craving.

We hypothesize that the effects of progesterone on stress and craving will be stronger in women than in men.

3. Background:

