Results: Dually diagnosed veterans reported significantly more craving for alcohol when exposed to trauma imagery than when exposed to stressful or neutral imagery ($p<0.001$) (Figure 1). The stress response decreased with treatment, and those with high stress response on prazosin reported greater, but not statistically significant, change in their drinking at the end of treatment (Figure 2). Also, there was a significant relationship ($r=0.603$) (Figure 3) between craving and the number of drinking days at follow up.

Conclusions: The preliminary findings show that veterans with dual diagnosis report strong craving after exposure to trauma

related imagery. **Based on this result we eliminated the stress condition for the present study.** The trauma-induced response predicted drinking at the end of treatment and at follow up.

- *These finding support the notion that reactivity to stress may increase the susceptibility for relapse.*
- *This study demonstrates that we have experience with this paradigm.*
- *It validates the ability of our research team to recruit individuals with AUD and PTSD.*

4. Significance:

To our knowledge, this study is the first to examine the ability of progesterone to reduce trauma or stress-induced craving in individuals diagnosed with a) comorbid AUD and PTSD and b) AUD only. Positive findings from this study will: 1) provide evidence that progesterone is important in mediating stress and alcohol craving, 2) provide insight into the underlying mechanisms of stress and alcohol craving, 3) help identify a potential marker that will distinguish who may be at

higher risk for alcohol relapse, and 4) provide a platform for other exploratory studies that can include the use of progesterone as treatment options for AUD and PTSD.

5. Research Plan:

Participants: Participants (N=72 completers) will be eligible for the study if they fullfill the following criteria:

Inclusion criteria:

- a) men (n=36) and women (n=36) age 21 to 60;
- b) have current diagnosis of *either*:
 - 1. AUD and comorbid PTSD
 - OR
 - 2. AUD

AUD will be determined by Structured Clinical Interview for DSM-5 (SCID-5) (First, Spitzer, Gibbon, & Williams, 2015). PTSD will be determined by Clinician Administered PTSD scale (CAPS-5)(Weathers et al., 2013) and by SCID-5);

- c) drink regularly (determined by TLFB and recorded 90 days prior to the interview);
- d) are not in an active phase of alcohol withdrawal;

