- e) are not at risk for suicide; if on medication, they must be on a stable dose for at least 2 weeks;
- f) for women, have regular menses every 25-35 days.

Exclusion Criteria:

- a) current SCID diagnosis of any psychotic disorder; substance use disorder (other than alcohol, nicotine, and marijuana) in the past 30 days;
- b) current unstable medical condition; positive test results at more than one baseline appointment on urine drug screens conducted for opiates, cocaine, benzodiazepines, and barbiturates (marijuana is allowed);
- c) for women, amenorrhea, use of oral contraceptives;
- d) known allergy to progesterone or peanuts (vehicle for micronized progesterone);
- e) history of thrombophlebitis, deep vein thrombosis, pulmonary embolus, clotting or bleeding disorders, heart disease, or history of stroke.

Methods: All participants will complete 1 test day. In order to control for gender differences in progesterone levels we will test women in the follicular phase of the menstrual cycle. This experiment is a between-subject design. Before the test day every participant will receive either progesterone (200 mg. bid) or placebo in identical looking capsules for three days. In previous studies with addicted individuals, this dosing schedule of progesterone attenuated stress-induced craving and improved cognitive function(Fox et al., 2013; Sofuooglu et al., 2011). On the fourth day they will attend the laboratory session. The study will consist of four phases. 1) We will first recruit participants, obtain informed consent, and evaluate eligibility for the study. 2) Following completion of intake assessments, participants will receive a full physical examination to further determine eligibility. 3) If eligible they will be randomized to start pre-treatment with either progesterone or placebo and scheduled for the laboratory session. 4) Follow-up: Participants will be contacted approximately 1 day after completing the stress lab to see how they are doing and to answer questions about their drinking. They will also be asked to come for one follow up session 1 month later to determine their drinking habits following the lab session.

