Medication: All participants will be asked to take progesterone or placebo for three days leading up to the laboratory test day. They will be asked to take the first dose of medication

(progesterone or placebo) at night to minimize possible sedation from progesterone treatment. The following morning they will come to the clinic to take the second dose in the morning and will be given three additional doses (one to take at night the same day and two doses – morning and night for the following day). On the fourth day they will come in the morning for the laboratory session and will take one last dose in the lab. For women, the treatment will be initiated within the first 4 days of the menstrual cycle, day one being the first day of menses, and will be completed within the early follicular phase.

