Laboratory sessions: Laboratory sessions will be conducted on the Biological Studies Unit at the West Haven VA with trained personnel, and a psychologist or MD will be on call during the laboratory session. Additionally, all participants will be cleared by a study doctor prior to leaving the lab at the end of the imagery session (see Table 1 for details). Participants will be asked to arrive around 10:00 am. On arrival there will be a urine and breath alcohol concentration (BrAC) check. If clear to start an IV line will be placed. Those who test positive for any substance (other than marijuana) will be discharged. Blood pressure and pulse will be monitored continuously. Subjective measures of craving for alcohol, anxiety, affect, and cognitive functioning will be administered shortly after the set up. Prior to the presentation of the 1st and 2nd tapes, the relaxation technique will be used. Two conditions will be administered in a counterbalanced order: Trauma/Stress script and Neutral script. Subjective measures of craving, anxiety, affect, and cognitive functioning will be presented:1) prior to presentation of the scripts, b) immediately after presentation of each script, and c) following a 5 minute recovery period. After the last recovery period and assessments subjects will be encouraged to use the relaxation techniques. Craving and emotional distress will be evaluated throughout the session and subjects must return to baseline levels prior to being discharged from the unit. Subjects will wear an ambulatory physiological monitor (APM) (Eqvital EQ02, Vivonoetics, San Diego, CA) that collects continuous ECG, respiration, and activity for 20 minutes while at quiet rest at baseline, and throughout the stress challenge procedure. After completion of the scheduled portion of a session, any subject that reports residual craving or distress will participate in guided relaxation procedures with a clinically-trained psychologist for up to one additional hour. Relaxation has also been shown to reduce PTSD symptoms(Hamid & Neissi, 2009). If craving or emotional distress persists after an hour of relaxation training, the subject will receive an individual counseling session with a psychologist who is experienced in psychotherapy for PTSD. If craving or emotional distress persists after the psychotherapy session, the subject will be escorted to the Emergency Department and treated by the on-call psychiatrist.

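### Participants who test positive on arrival leave after randomisation and dosing, with no craving data and no scheduled route into the drinking outcome

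*Combined protocol and SAP*

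**What the plan says.** All references are to the combined protocol and SAP.

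- **Randomisation** (section 5, Methods): "If eligible they will be randomized to start pre-treatment with either progesterone or placebo and scheduled for the laboratory session".
- **Dosing** (section 5, Medication): "All participants will be asked to take progesterone or placebo for three days leading up to the laboratory test day". The schedule there gives five doses before the laboratory day and a last one in the laboratory.
- **Arrival test** (section 5, Laboratory sessions): "On arrival there will be a urine and breath alcohol concentration (BrAC) check". Then: "Those who test positive for any substance (other than marijuana) will be discharged". Rescheduling is not mentioned.
- **Craving** (section 5, Laboratory sessions and Table 1): all the craving ratings come after this check.
- **Follow-up** (section 5, Methods): "Participants will be contacted approximately 1 day after completing the stress lab". Participants are also asked to "come for one follow up session 1 month later to determine their drinking habits following the lab session". Under Subjective Outcome Measures, TLFB is placed at screening, at the laboratory session and one month after it.
- **Drinking aim** (section 2, Exploratory Aims): whether progesterone is "more effective than placebo in reducing drinking and relapse during one month" after exposure to the cues.
- **Sample** (section 5, Participants): "N=72 completers". Power Analysis allows for 20% dropout without saying what counts as dropout.
- **Analysis** (section 5, Method for data collection and analyses): mixed effects models are named. No analysis set, missing-data rule or handling of discharged participants is given.

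**The concern.** This loss is not ordinary dropout. Being discharged depends on drinking or drug use in the preceding hours or days, at a time when participants are already on progesterone or placebo. The trial enrols regular drinkers with alcohol use disorder, and its hypotheses are that the drug lowers craving and perhaps drinking. Some positives are foreseeable: the drug-screen exclusion applies only to people positive at more than one baseline appointment.

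Two outcomes are affected. For craving, a discharged participant contributes no laboratory ratings, and a mixed model cannot recover someone with no outcome rows. For drinking, the people who drank or used drugs shortly before the laboratory day are the ones for whom no further contact is scheduled. If progesterone works as hypothesised, more of them would come from the placebo arm. The remaining placebo participants would then look better than the arm that was randomised, and a real effect could be understated.

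**Working it through.** **1. Order of events.** Randomise, give five doses, test on arrival, discharge if positive, then measure craving. Selection therefore takes place after randomisation and after exposure to treatment. The next-day contact, the 1-month visit and the two later TLFB assessments are each dated from the laboratory session, so a discharged participant has no date from which any of them would run.

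**2. The plan's own figures.** The plan gives no discharge rate. Its sample size of 30 is close to a paired normal calculation: ((1.960 + 0.842)/0.50)² = 31.4, so 32, with 78.2% power at 30. The figure of 36 recruited is 30 × 1.2; dividing instead gives 30/0.8 = 37.5, so 38. The planned effect of 0.50 is labelled within-subject, so it is only a rough yardstick for a difference between arms.

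**3. Illustrative bias in craving level.** Assumptions, none of them in the documents:

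- Latent drinking L is standard normal, and the heaviest drinkers in each arm are the ones discharged.
- Craving correlates 0.3 to 0.6 with L. The pilot's r = 0.603 lends loose support to the upper value, but it relates craving to later drinking days and comes from a study with 18 completers.
- 10% are discharged on progesterone and 20% or 30% on placebo.

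Among those who stay, E[L | L < c] = −φ(c)/Φ(c):

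- 10% removed: c = 1.282, −0.1755/0.90 = −0.195
- 20% removed: c = 0.842, −0.2800/0.80 = −0.350
- 30% removed: c = 0.524, −0.3477/0.70 = −0.497

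The bias (progesterone minus placebo) is the difference in these means times the correlation. Products use unrounded values.

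| Placebo vs progesterone discharged | Difference in mean L | Bias at 0.3 | Bias at 0.6 | Size relative to 0.50 |
|---|---|---|---|---|
| 10% vs 10% | 0 | 0 | 0 | 0% |
| 20% vs 10% | 0.155 | 0.046 SD | 0.093 SD | 9–19% |
| 30% vs 10% | 0.302 | 0.091 SD | 0.181 SD | 18–36% |
| 10% vs 20% | −0.155 | −0.046 SD | −0.093 SD | 9–19%, reversed |

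A positive value makes progesterone look worse than it is. The last row shows that the sign follows whichever arm loses more participants.

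**4. How demanding the scenarios are.** With one discharge threshold for both arms, 20% vs 10% implies that progesterone shifts latent drinking by 1.282 − 0.842 = 0.44 SD within about three days. For 30% vs 10% the shift is 1.282 − 0.524 = 0.76 SD, more than the 0.50 planned for craving. If 72 participants split into 36 per arm, the standard error of a standardised difference is √(2/36) = 0.24, so the range above is roughly 0.2 to 0.8 standard errors.

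**The case against.** The strongest reply is that the documents are silent on this group and do not exclude it. No sentence limits follow-up to people who finished the laboratory session, and the request to attend at one month carries no completion condition. The word discharged is not defined; later in the same paragraph it describes leaving the unit at the end of an ordinary session. A reader might infer that the plan forbids following these participants, and the text does not support that. What stands is narrower: the schedule supplies no contact for them, because every later contact is dated from the session.

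A reader might also take the 72 completers as an analysis set restricted to completers. The phrase sits in the Participants paragraph as a recruitment target, and the dropout allowance may already include laboratory-day losses.

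The drinking aim is exploratory and is defined from exposure to the cues. A discharged participant was not exposed and has no start date under that definition. This is correct, and it means that keeping them requires a new time origin and answers an additional question.

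The bias range is also open to challenge. It assumes unequal discharge and strict removal of the heaviest drinkers. A morning breath test with a urine screen is a noisier filter, and noise shrinks the bias. The primary model compares conditions and time points within a person, so stable differences in craving level largely cancel; the assumed correlation has not been shown for reactivity. These objections limit the size. They do not remove the selection after randomisation.

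**Conclusion.** The concern holds as a gap in the design that is cheap to close. Following the plan as written drops a group defined by substance use after randomisation from the craving data, and leaves it without a scheduled place in the drinking data. If discharge differs between arms, or removes different kinds of people from each, the comparison is no longer fully randomised.

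Under the trial's hypothesis the bias would run toward no effect, so this is mainly a risk of missing or understating a benefit. The size is unknown. It is about zero if discharge is equal and similar in the two arms. The 0.05–0.18 SD range is an illustrative upper range for craving level and is probably smaller for within-subject reactivity. It would be tempting to say that the plan loses 9–36% of its planned effect. The documents do not support that: they give no discharge rates, and the 0.50 is a within-subject figure. No corresponding figure can be given for the drinking outcome.

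**What to change.** Leave the discharge rule unchanged and add the following to section 5.

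1. Keep every randomised participant, including those discharged on arrival, in the next-day contact and the 1-month TLFB visit. State what discharged means for study participation.
2. Count drinking from randomisation or from the scheduled laboratory day (choose one in advance) and compare it by randomised arm. Keep the stated post-exposure analysis for those who completed the laboratory session.
3. Report the number of laboratory-day positives by arm. This shows directly whether the arms were selected differently.
4. Optionally, add a sensitivity analysis for the missing craving data over a range of shifts stated in advance. A single unexplained shift would add little.

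The cost is a few visits at the planned $50 payment. Under the illustrative rates with 36 per arm, the discharged number 36 × 0.20 + 36 × 0.10 = 10.8 to 36 × 0.30 + 36 × 0.10 = 14.4, or roughly $540 to $720 in payments. Some discharged participants will not return, and the new drinking comparison answers a post-randomisation question alongside the post-exposure one. If the sponsor already intends to follow this group, item 1 needs only a clarifying sentence.

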Table 1. Summary of procedures and measures during the test day
(Note: all times are approximate)

Condition	Event	Measures		
		Biochemical	Physiologic	Subjective
Baseline	Time			
	10:00 am	Baseline measures Study medication administration	Urine, BrAC, Blood collection for: progesterone, ALLO, and estradiol (women)	HR/BP APM
	11:30 am	Meal		
Tape 1	11:50 am	Relaxation period		
	12:00 pm	Measures before presentation of 1 st tape		HR/BP APM

	12:20 pm	Presentation of 1 st tape		HR/BP APM	
	12:25 pm	Measures after 1 st tape		HR/BP APM	VASC, AUQ, VASA, STAI, DES-R, Stroo
	12:45 pm	Recovery		HR/BP APM	
	12:50 pm	Measures after recovery		HR/BP APM	VASC, AUQ, VASA, STAI, DES-R, Stroo
	1:10 pm	5 minute break			
Tape 2	1:15 pm	Relaxation period			
	1:25 pm	Measures before presentation of 2 nd tape		HR/BP APM	VASC, AUQ, VASA, STAI, DES-R, Stroo
	1:45 pm	Presentation of 2 nd tape		HR/BP APM	
	1:50 pm	Measures after 2 nd tape		HR/BP APM	VASC, AUQ, VASA, STAI, DES-R, Stroo
	2:10 pm	Recovery		HR/BP APM	
	2:15 pm	Measures after recovery	Blood ALLO	HR/BP APM	VASC, AUQ, VASA, STAI, DES-R, Stroo

Progesterone:

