Progesterone, a natural hormone, is safe and well-tolerated by women. The safety, tolerability and efficacy of micronized progesterone is well established and it is FDA approved for hormone replacement therapy (HRT), absence of menstrual periods (amenorrhea), and infertility treatment. The recommended dose of progesterone for hormone replacement treatment is 200 to 400 mg/day, given as a single evening dose. After oral administration, micronized progesterone reaches its peak plasma levels in two to three hours and has an elimination half-life of three to four hours (McAuley *et al*, 1996). Because of its short half-life progesterone will be given twice daily to maintain stable plasma levels. Progesterone doses higher than 400 mg/day will not be used since they are more likely to cause sedation. The safety and tolerability of micronized progesterone are well established. Others have used micronized progesterone in several previous studies with male and female smokers and cocaine users (Sofuooglu *et al*, 2001; Sofuooglu *et al*, 2009; Sofuooglu *et al*, 2011). Progesterone was well-tolerated and there were no serious adverse events. The most common adverse effect is mild sedation. Other less common adverse effects include menstrual irregularity, spotting or breakthrough bleeding, dizziness, cramps, nausea, fatigue, headache, an allergic reaction, and breast tenderness. Other side effects attributed to synthetic progestin, including depression, fluid retention, pruritus, jaundice, rash and thrombotic disorders have not been observed with natural progesterone. Women will be warned to use caution when driving a motor vehicle or operating machinery while undergoing study treatment.

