Method for data collection and analyses: Prior to performing statistical analyses, we will calculate descriptive statistics and will assess whether the distributions of all measures conform to normality. We will apply transformation or use nonparametric methods as necessary. We will estimate effect sizes in order to inform the design of potential future definitive studies. For the primary hypotheses we will use mixed effects models to assess change in stress reactivity after administration of progesterone vs. placebo. Study medication (progesterone and placebo), and gender will be a between subject factors, condition (trauma vs neutral) and time (pre, post and recovery following script presentation) will be used as within-subject factors. The primary stress reactivity variables will be craving. We will first compute descriptive statistics for each variable and will assess data distributions. All tests will be two-sided at 0.05 level of significance. We will use the Schwartz-Bayesian criterion (BIC) to select the best-fitting correlation structure within subject.

Study Duration: Two years.

6. References:

Allen, M. T., Boquet, A. J., Jr., & Shelley, K. S. (1991). Cluster analyses of cardiovascular responsivity to three laboratory stressors. *Psychosomatic Medicine*, 53(3), 272-288.

Blake, D. D., Weathers, F. W., Nagy, L. M., Kaloupek, D. G., Klauminzer, G., Charney, D. S., & Keane, T. M. (1990). A clinician rating scale for assessing current and lifetime PTSD: The CAPS-1. *Behavior Therapy*, 13, 187-188.

Bohn, M. J., Krahn, D. D., & Staehler, B. A. (1995). Development and initial validation of a measure of drinking urges in abstinent alcoholics. *Alcoholism, Clinical and Experimental Research*, 19(3), 600-606.

Brady, K. T., Killeen, T., Saladin, M. E., Dansky, B., & Becker, S. (1994). Comorbid Substance-Abuse and Posttraumatic-Stress-Disorder - Characteristics of Women in Treatment. *American Journal on Addictions*, 3(2), 160-164.

Breese, G. R., Chu, K., Dayas, C. V., Funk, D., Knapp, D. J., Koob, G. F., . . . Weiss, F. (2005). Stress enhancement of craving during sobriety: a risk for relapse. *Alcoholism, Clinical and Experimental Research*, 29(2), 185-195.

Bremner, J. D., Krystal, J. H., Southwick, S. M., & Charney, D. S. (1996). Noradrenergic mechanisms in stress and anxiety: II. Clinical studies. *Synapse*, 23(1), 39-51. doi: 10.1002/(SICI)1098-2396(199605)23:1<39::AID-SYN5>3.0.CO;2-1

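### Script order is assigned by the trial but is missing from the primary craving model and is not stated to be balanced within medication arm: a conditional loss of precision, not a bias

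*Combined protocol and SAP*

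**What the plan says.** Under 5. Research Plan, Laboratory sessions: "Two conditions will be administered in a counterbalanced order: Trauma/Stress script and Neutral script". The Methods paragraph gives each participant a single test day, so both scripts fall in the same session. Randomization is described there for medication only: "If eligible they will be randomized to start pre-treatment with either progesterone or placebo and scheduled for the laboratory session". Neither paragraph says at what level order is counterbalanced.

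The primary model is in Method for data collection and analyses: "Study medication (progesterone and placebo), and gender will be a between subject factors", and "condition (trauma vs neutral) and time (pre, post and recovery following script presentation) will be used as within-subject factors". Time there means the measurement point around a script, so it does not stand for first or second tape. No sensitivity analysis mentions order. The covariance is chosen from the data: "We will use the Schwartz-Bayesian criterion (BIC) to select the best-fitting correlation structure within subject".

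Table 1, whose times are all approximate, has a 10:00 am row reading "Baseline measures Study medication administration". The first tape is at 12:20 pm, and "presentation of 2 nd tape" is at 1:45 pm. The Progesterone section states that "micronized progesterone reaches its peak plasma levels in two to three hours and has an elimination half-life of three to four hours".

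**The concern.** Order is a factor that the trial itself sets, and each tape position is a different point in a session of several hours. Habituation, fatigue, carry-over from the first script or time since the dose could each make reactivity differ between tapes. A shift that raises the pre and post measures of a tape equally cancels from the pre-to-post change. A position effect on the change itself does not cancel. Unmodelled, it enters the error of the medication x condition x time contrast, which carries the primary craving hypothesis. If order is balanced only over the whole sample, the arms can also differ in order by chance.

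**Working it through.** **Inputs.** d=0.5, two-sided alpha 0.05 and 30 per group come from Power Analysis and from Method for data collection and analyses. Participants gives 72 completers. Assumptions: 30 per medication arm (the plan does not define group), or 36 per arm (72 split 1:1); d=0.5 applied to the contrast below; position effects p of 0.1, 0.25 and 0.5 SD.

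**1. The plan's own figure.** A paired normal calculation gives n = (1.960 + 0.842)² / 0.5² = 31.4, and power of 78.2% at n=30, close to the stated 80%. That is a within-subject calculation. Medication is compared between subjects, where a two-sample t-test at d=0.5 has 47.8% power with 30 per arm and 55.3% with 36. That mismatch is a separate matter; these values are only the baseline for what follows.

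**2. Set-up.** Let D = (post − pre) for trauma minus (post − pre) for neutral, with SD 1. Let the second tape add p to its post measure. D then shifts by +p when trauma is second and by −p when it is first, so the order groups differ by 2p (0.2, 0.5, 1.0 SD).

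**3. Model-based standard error with order omitted.**
- Unstructured covariance: the variance of D becomes 1 + p², so the SE is multiplied by √(1+p²) = 1.005, 1.031, 1.118.
- Random intercept: D weights four measures by ±1, so the residual variance is 1/4. Omitting order leaves ±p/2 on one post measure and the opposite on the other. The sum of squares is p²/2; spread over five within-subject contrasts this is p²/10, or 0.4p² relative to 1/4. The SE multiplier is √(1+0.4p²) = 1.002, 1.012, 1.049.

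**4. Bias.** With order balanced within arm, the shifts average to zero in each arm. With balance only overall, they average to zero over possible lists. In the difference-score simulations the mean bias was within 0.003 SD of zero throughout. A single list can still be unlucky. With 36 of 72 trauma-first overall, the chance that an arm has 21 or more, or 15 or fewer, is 24%. A 21 versus 15 split moves the contrast by (6/36 + 6/36)p = 0.33p.

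**5. Type I error at p=0.5, order omitted.**
- Balanced within arm: the true SE is not inflated but the reported one is. Unstructured: 1.96 × 1.118 = 2.19, about 2.8%. Random intercept: 1.96 × 1.049 = 2.06, about 4.0%. Simulation gave 2.8–2.9% and 3.9–4.0% (2.4% in a difference-score run with 36 per arm).
- Balanced only overall: the true variance is 1.25 on average. The unstructured model estimates that, and simulated error is 4.7–5.1%. The random-intercept model reports 1.10, so the effective cut-off is 1.96 × √(1.10/1.25) = 1.84, about 6.6%. Simulations ranged from 6.2% to 6.9%. At p=0.25 the figure is 5.4–5.5%.
- With the order terms: 4.8–5.2%.

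**6. Power, six-measure model, order balanced within arm, d=0.5, order omitted vs modelled.**

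| p (SD) | 30 per arm, unstructured | 30 per arm, random intercept | 36 per arm, unstructured |
|---|---|---|---|
| 0.1 | 47.4 vs 47.7% | 48.7 vs 48.8% | 54.6 vs 55.0% |
| 0.25 | 45.7 vs 48.2% | 48.2 vs 49.3% | 53.0 vs 55.4% |
| 0.5 | 39.0 vs 48.1% | 45.1 vs 49.2% | 45.8 vs 55.4% |

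If group means diagnosis, split 1:1 by medication, there are 15 to 18 per arm. The unstructured figures at p=0.5 are then 19.0 vs 26.1% and 22.8 vs 30.8%.

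**7. Effect in the progesterone arm only** (difference score, 30 per arm, d=0.5). A common order term moves power from 42.3 to 44.9% at p=0.5, and from 46.4 to 47.0% at p=0.25.

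**8. Timing.** From 12:20 pm to 1:45 pm is 85 minutes. With a dose at exactly 10:00 am, the tapes fall 2 h 20 min and 3 h 45 min later. With a dose after 10:20 am, tape 1 comes less than 2 h later. With a dose at 10:45 to 11:15 am, tape 1 is at 1 h 35 min to 1 h 05 min and tape 2 at 3 h to 2 h 30 min.

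**The case against.** The best case for the plan is that counterbalancing is already there, the mean bias is zero, and the effect size is unknown. Relaxation before each tape, a recovery period, a break and fresh measures before the second tape make a large carry-over less likely. At 0.1 to 0.25 SD little is lost. With order balanced only overall and a random intercept, adding the term is roughly neutral for power until 0.5 SD (48.4 vs 47.8%, 47.3 vs 47.6% and 45.9 vs 48.6% at 0.1, 0.25 and 0.5 SD). All of this stands, and it limits the point to a low-cost improvement. It does not remove it: the safeguards act mainly on level, a change in reactivity can remain, and the last comparison is between an omitted-order test whose type I error is inflated and one that holds its level.

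Three stronger readings do not hold.
- *The medication effect is biased.* Nothing suggests that order depends on arm.
- *Tape 1 falls at the plasma peak and tape 2 after it.* That needs a dose at exactly 10:00 am. Participants arrive at about that time, then have urine and breath checks and an IV line placed, and Table 1 puts baseline measures and dosing in one row. Step 8 shows that a later dose reverses the picture. No section links plasma level to craving reactivity.
- *The plan stands to lose 9 to 10 points of power.* That needs 0.5 SD in both arms and unstructured covariance. A time-since-dose effect would act in the progesterone arm only, where the common term recovers about 1 to 3 points even at 0.5 SD.

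**Conclusion.** The point holds in a conditional form. The trial assigns script order, the listed primary-model factors leave it out, and balance within medication arm is not stated. If position affects reactivity, the test of medication is not biased on average. Its standard error, however, is too large (balanced within arm), needlessly large (balanced overall, unstructured) or too small (balanced overall, random intercept). The consequence is negligible at 0.1 SD and small at 0.25 SD, and becomes material only towards 0.5 SD, where the order groups differ by a full SD. Its size there depends on the covariance that BIC selects. In the simulated data BIC always chose the random intercept, but those data were generated with one, so both structures are shown. The results rest on assumed position effects, complete data, d=0.5 on the contrast and the per-arm sizes above. This is a worthwhile, near-free gain in precision and error control. It does not correct a biased analysis.

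**What to change.** 1. Generate the order list so that trauma/stress-first and neutral-first are balanced within medication arm, and record the order for each participant.
2. Prespecify order and order x condition (which is tape position), each with its time interaction, as fixed effects in the primary craving model. A position main effect alone would absorb only level shifts.
3. Add a medication x position term as a sensitivity analysis, since time since dose may differ between tapes in the progesterone arm.

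Cost: a few lines in the analysis section, one balancing factor and one recorded variable. The model gains six fixed-effect parameters (1 + 1 + 2 + 2), from 24 to 30 if medication, gender, condition and time are fully crossed, and loses one residual degree of freedom on the tested contrast under unstructured covariance. With order balanced within arm and no position effect, power is unchanged (47.5 vs 47.5% at d=0.5, 30 per arm). If order is balanced only overall and there is no position effect, the terms cost up to about 0.8 points, so steps 1 and 2 belong together.
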